Hypothesis: Oral selinexor + standard of care (SoC) will expedite the recovery, suppress the viral load, shorten the hospitalization and reduce morbidity and mortality in patients with severe COVID-19 compared to placebo + SoC.

**Objectives and Endpoints:** Low dose oral selinexor (20 mg on QoD each week) + SoC will expedite the clinical recovery, suppress the viral load, shorten the hospitalization and reduce morbidity and mortality in patients with severe COVID-19 compared to placebo + SoC.

| Objectives                             | Endpoints   |
|--|---|
| Primary Objectives              |   |
| Day 14 Ordinal Scale Improvement (OSI) | Proportion of patients with at least a 2 point improvement (increase) in the Ordinal Scale from baselineto Day 14.

The Ordinal Scale is an assessment of the clinical status at the first assessment on each day of hospitalization.

The scale is as follows: 
 
1. Death;
 
2. Hospitalized, on invasive mechanical ventilation or extracorporeal membrane oxygenation (ECMO);
 
 |

|  |   |
|--|---|
|  | 
 
3. Hospitalized, on non-invasive ventilation or high flow oxygen devices;
 
4. Hospitalized, requiring supplemental oxygen;
 
5. Hospitalized, not requiring supplemental oxygen - requiring ongoing medical care (COVID-19 related or otherwise);
 
6. Hospitalized, not requiring supplemental oxygen - no longer requires ongoing medical care;
 
7. Not hospitalized, limitation on activities and/or requiring home oxygen;
 
8. Not hospitalized, no limitations on activities.
 
  |
| Key Secondary Objectives  |   |

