### **4.4 Missing Data Handling Rules**

Unless otherwise stated, missing data will not be imputed.

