**Table 6: Efficacy Endpoints and Definitions**

Endpoint	Definition
Primary Endpoint	
Day 14 Ordinal Scale improvement (OSI2-14)	Proportion of patients with at least a 2 points improvement (increase) in the Ordinal Scale by Day 14. Baseline score is defined as the last score measured before first dosing. The improvement is assessed between the baseline score and the latest score on or before Day 14, End of study (EoS) date, or database cut date, whichever occurs first.
Key Secondary Endpoints	
Time to an improvement of 2 points using Ordinal Scale (TTCI-2)	The time from randomization to an improvement of 2 points on the Ordinal Scale. For patients who didn't achieve clinical improvement of 2 points, 
 
If no death event by Day 28, they will be censored on the last contact date, on or before Day 28, EoS date, or database cut date, whichever occurs first.
 
 If they died by Day 28, they will be censored on Day 28.
Overall death rate on Day 28 (DR-28)	Proportion of patients died on or before Day 28.
Rate of mechanical ventilation (RMV)	Proportion of patients who ever used invasive mechanical ventilation or ECMO during the hospital stay.
Time to mechanical ventilation (TTMV)	Time to the first use of mechanical ventilation. For patients who never used mechanical ventilator, the censoring date is defined as the death date or last contact date (if no death), on or before EoS or database cut date, whichever occurs first.

Additional Secondary Endpoints	
Time to recovery (TTR)	Time to improvement from baseline score of 3 to $\geq 4$ or from a baseline score of 4 to $\geq 5$ by Day 28. For patients who didn't achieve recovery, the censoring rule will be the same as that in TTCI-2.
Day 7 Ordinal Scale 2 points improvement (OSI2-7)	Proportion of patients with at least a 2 points improvement (increase) in the Ordinal Scale from baseline to Day 7. The improvement is assessed between the baseline score and the latest score on or before Day 7, End of study (EoS) date, or database cut date, whichever occurs first.
Day 7 Ordinal Scale 1 point improvement (OSI1-7)	Proportion of patients with at least a 1 point improvement (increase) in the Ordinal Scale from baseline to Day 7. The improvement is assessed the same as in OSI2-7.

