Day 14 Ordinal Scale 1 point improvement (OSI1-14)	Proportion of patients with at least a 1 point improvement (increase) in the Ordinal Scale from baseline to Day 14. The improvement is assessed the same as in OSI2-14.
Time to an improvement of 1 point on the Ordinal Score (TTCI-1)	The time from randomization to an improvement of 1 point on the Ordinal Scale. For patients who didn't achieve clinical improvement of 1 point, the censoring rule will be the same as that in TTCI-2.
Overall survival (OS)	Time since randomization to death date, or the last contact date with patient status being alive, on or before EoS or database cut date, whichever occurs first.
Overall death rate on Day 14 (DR-14)	Proportion of patients died on or before Day 14.
Rate of ICU admission	Proportion of patients with ICU admission.
Length of hospitalization	Length of hospital stay defined as cumulative length of hospital stay.
Length of ICU stay	Cumulative length of ICU stay.
Duration of mechanical ventilation	Cumulative number of days with invasive mechanical ventilation or ECMO

PaO 2 :FiO 2 and/or oxygenation index over time	PaO 2 :FiO 2 and/or oxygenation index over time. Will be summarized by visit using descriptive statistics.
---	--

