### **7.2.2 Analyses of Additional Secondary Endpoints**

For the additional secondary endpoints, binary endpoints and time to event endpoints will be analyzed similarly as for the key secondary endpoints, with the only exception that there will be no hypothesis testing.

For continuous endpoints (length of hospitalization, length of ICU stay, duration of mechanical ventilation), summary statistics by treatment arm will be provided including number of patients, median, mean, standard deviation, minimum, and maximum.

For duration of mechanical ventilation, sensitivity analyses will be performed in the same manner as RMV.

For PaO2:FiO2 and/or oxygenation index over time, only descriptive statistics will be provided.

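### Length of hospitalization is summarised as raw cumulative days with no rule for death, so when deaths come before typical discharge the arm with more deaths can show the shorter mean stay

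*SAP*

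**What the plan says.** SAP Table 6 lists three durations among the additional secondary endpoints:

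- hospitalization: "Length of hospital stay defined as cumulative length of hospital stay"
- ICU: "Cumulative length of ICU stay"
- ventilation: "Cumulative number of days with invasive mechanical ventilation or ECMO"

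None of the three has a rule for death, a start point or a time horizon.

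SAP 7.2.2 gives the analysis: "For continuous endpoints (length of hospitalization, length of ICU stay, duration of mechanical ventilation), summary statistics by treatment arm will be provided". Additional secondary endpoints are handled like the key secondary ones "with the only exception that there will be no hypothesis testing". SAP Table 5 assigns them to the ITT population, and descriptively to the Proof of Concept cohort, so patients who die stay in the summaries. The only sensitivity analysis for any of the three is for ventilation duration. It widens the kinds of respiratory support counted and does not concern death. The general rule in SAP 4.4 is "Unless otherwise stated, missing data will not be imputed", so no value is assigned after death by default.

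Elsewhere in Table 6 the SAP does write a death rule. For TTCI-2, patients without the improvement are treated as follows: "If they died by Day 28, they will be censored on Day 28". TTR and TTCI-1 adopt the same rule; the three durations do not refer to it.

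The hypothesis in the Protocol Synopsis is that selinexor with standard of care will "suppress the viral load, shorten the hospitalization and reduce morbidity and mortality". Protocol 1.3 repeats the aim of shortening hospitalization.

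**The concern.** In a raw count of hospital days, a patient who dies on Day 4 and a patient discharged well on Day 4 contribute the same value. If one arm has more deaths and those deaths come sooner than a typical discharge, its mean stay falls for that reason alone. The plan's only direct measure of a hypothesised benefit could then favour the arm that did worse.

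The summaries are untested, but they will be seen: Protocol 10.6 commits the sponsor to posting secondary endpoint results publicly. A reader given a mean stay and a death rate in separate tables cannot work out a death-adjusted stay from them. TTCI-2, TTR and TTCI-1 avoid counting death as a quick success, so the same table treats death inconsistently.

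**Working it through.** The plan gives no expected value, power or sample size for the three durations, so there is no figure to reproduce. All day counts and death rates below are assumptions; only the formulas are general.

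**1. Hospital stay, by formula.** Let p be an arm's death rate, Ls the mean stay of survivors and Ld the mean stay of patients who die. The raw arm mean is (1 − p) × Ls + p × Ld. With Ls and Ld the same in both arms,

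difference in mean stay = −(difference in p) × (Ls − Ld).

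Take Ls = 12 days and a death rate 10 points higher in one arm:

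| Ld (days) | Calculation | Shift in the arm with more deaths |
|---|---|---|
| 4 | −0.10 × (12 − 4) | −0.8 day |
| 7 | −0.10 × (12 − 7) | −0.5 day |
| 12 | −0.10 × (12 − 12) | 0 |
| 18 | −0.10 × (12 − 18) | +0.6 day |

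The Ld = 7 row, written out for mortality 20% vs 10%:

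- Raw mean: 0.8 × 12 + 0.2 × 7 = 11.0 days, against 0.9 × 12 + 0.1 × 7 = 11.5 days. The arm with more deaths looks 0.5 day better.
- Days alive and out of hospital to Day 28, death scored 0: 0.8 × (28 − 12) = 12.8, against 0.9 × 16 = 14.4. The same arm is 1.6 days worse.

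**2. Hospital stay, by simulation.** There were 400,000 patients per arm with the same lognormal survivor stay in both arms (median 8, 10 or 14 days, log-SD 0.6). Mortality was 15% in one arm and 20% or 25% in the other. Death days were uniform over the window shown. Differences are the arm with more deaths minus the other; ranges run over the survivor medians and both mortality levels.

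| Days of death | Raw mean stay | Raw median stay | Hospital-free days, death = 0 |
|---|---|---|---|
| 1–5 | −0.34 to −1.41 | 0 to −2 | −0.62 to −1.80 |
| 2–8 | −0.25 to −1.19 | 0 to −2 | −0.64 to −1.82 |
| 5–15 | +0.01 to −0.71 | 0 | −0.58 to −1.78 |
| 10–28 | +0.08 to +0.88 | 0 to +1 | −0.61 to −1.78 |

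The raw mean changes sign with the timing of death. The death-aware measure is worse for the arm with more deaths in every row.

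**3. Ventilation duration.** Assume survivors are ventilated for 12 days and 20% of each arm is ventilated.

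- *Same patients ventilated, more of them die* (60% vs 35%). Among ventilated patients the shift is −0.25 × (12 − Ld): −2.0 days at Ld = 4 and −1.0 at Ld = 8. Over all ITT patients, multiply by 0.20: −0.4 and −0.2 day. At Ld = 16 the signs reverse, to +1.0 and +0.2 day.
- *Five points of the arm are newly ventilated and die.* For simplicity, the other 20% are ventilated for 12 days in both arms. The ITT mean rises from 0.20 × 12 = 2.4 to 2.4 + 0.05 × 4 = 2.6 (Ld = 4) or 2.4 + 0.05 × 8 = 2.8 (Ld = 8), a shift of +0.2 or +0.4 day. Among ventilated patients the mean falls to 2.6 / 0.25 = 10.4 or 2.8 / 0.25 = 11.2, a shift of −1.6 or −0.8 day.

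In the second case the same data give opposite signs according to the denominator. No separate calculation was run for ICU stay. Its definition has the same structure, so it depends in the same way on death timing and denominator.

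**The case against.** The case against giving this much weight is substantial, and most of it stands.

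- **The consequence is contained.** These are descriptive additional secondary endpoints outside the testing sequence. Mortality is reported as DR-28, DR-14 and OS. Death is the worst ordinal category, so it cannot count as improvement in the primary endpoint.
- **A large mortality gap would not pass unnoticed.** Protocol 9.5 sets a halt for a death-rate difference above 10 points once more than 120 patients are enrolled, so the 10-point illustration sits at that threshold.
- **The distortion is small against sampling noise.** A lognormal stay with median 10 and log-SD 0.6 has SD 10 × exp(0.18) × √(exp(0.36) − 1) ≈ 7.9 days. With about 123 per arm (roughly half of 247), the standard error of a difference is about 7.9 × √(2/123) ≈ 1.0 day. A 0.5-day shift is about half of that.
- **Raw stay answers a legitimate resource question,** and days alive and out of hospital is a different, composite measure. In the worked example its 1.6-day deficit comes wholly from mortality.

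A reader might also infer that all three durations always favour the arm with more deaths, or that medians fall along with means. The documents do not support either. They give no death timing, and late deaths reverse the sign. They do not state whether ICU and ventilation days are averaged over all ITT patients or only those admitted or ventilated. With every survivor at 12 days and 10–20% dying, both medians remain 12. Only hospital stay is named in the hypothesis; ICU stay and ventilation duration are not.

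These points limit the size and reach of the problem without supplying the missing rule. The exclusion of patients unlikely to survive 48 hours removes only the very earliest deaths. Separate mortality tables show that deaths differ, but not how far they have moved the mean stay.

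**Conclusion.** The point holds for length of hospitalization, on one condition: when deaths come before typical discharge, extra deaths shorten the raw mean stay, and the plan has no rule to prevent or reveal this. With 12-day survivors and 10 points more mortality, the shift runs from −0.8 day (decedents staying 4 days) through 0 (12 days) to +0.6 day (18 days). This assumes equal survivor stay in both arms, and the day counts and death rates are not from the documents.

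For ICU stay and ventilation duration the gap is the same, but the direction cannot be stated until the denominator is fixed.

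A reader might take this as a threat to the trial's conclusions. It is not: no alpha is spent on these endpoints, and the primary and key secondary results are untouched. What is at stake is a published descriptive summary, bearing on a stated hypothesis, whose direction depends on when patients die. That is worth correcting before unblinding.

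**What to change.** In SAP Table 6 and 7.2.2:

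1. Keep the three raw durations, but show them separately for survivors and decedents. State the start point and the denominator (all ITT, or only patients admitted to ICU or ventilated).
2. Add days alive and out of hospital, out of ICU and off ventilation, from randomization through Day 28, in all ITT patients, with death by Day 28 scored 0. Counting from randomization matters because SAP 4.2 sets Study Day 1 at first dose, which ITT patients who are never treated do not have.
3. Say how patients lost to follow-up before Day 28 are handled.

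Most of the data are already planned: admission date (Protocol 7.1.3), start and end of respiratory assistance (Protocol 7.3.1), weekly calls after discharge and survival status at Day 28 (Protocol Table 2). ICU dates are not itemised there, but the existing ICU endpoint already needs them.

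The cost is a little more programming. The added measures partly reflect mortality, so they should be presented beside DR-28 and not as separate evidence of faster recovery. Alpha, sample size and the primary analysis do not change.

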## 7.1 Analyses of Primary Efficacy Endpoint

The difference in OSI2-14 rates between treatment arms will be calculated with a 95% confidence interval (CI). Comparison between 2 treatment arms will be performed using the Cochran-Mantel-Haenszel (CMH) test stratified by the randomization stratification factors. The CMH estimate of the odds ratio and its 95% CI and the p-value for testing the treatment difference will be reported.

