**Efficacy Analyses:**

The difference of the primary endpoint (Day 14 OSI) between treatment arms will be calculated with a 95% confidence interval (CI). Comparison of OSI rates between the 2 treatment arms will be performed using the Cochran-Mantel-Haenszel (CMH) test stratified by the randomization stratification factors. The CMH estimate of the odds ratio and its 95% CI and the p-value for testing the treatment difference will be reported.

Analyses of other efficacy endpoints will be specified in [Section 9.4.1](#) and the SAP.

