| Complete Physical Exam                         | X          |                                   |           |           |           |            |            |             |             |            |            |                  | X                  |  |
| Pregnancy testing (per site guideline)         | X          |                                   |           |           |           |            |            |             |             |            |            | X                |                    |  |
| Ordinal Score d                     | X          | Daily and the day after discharge |           |           |           |            |            |             |             |            |            |                  | X                  |  |
| 12-lead ECG e                       | X          | As clinically indicated           |           |           |           |            |            |             |             |            |            |                  |                    |  |
| ABG (Arterial Blood Gas) f          | X          | As clinically indicated           |           |           |           |            |            |             |             |            |            |                  |                    |  |
| CBC with differential                          | X          | X                                 | X         | X         | X         |            | X          | X           | X           | X          | X          |                  | X                  |  |
| PT, aPTT, INR                                  | X          | X                                 | X         | X         | X         |            | X          | X           |             | X          | X          |                  |                    |  |
| Complete serum chemistry                       | X          | X                                 | X         | X         | X         |            | X          | X           | X           | X          | X          |                  | X                  |  |
| C-reactive protein, Ferritin, LDH g | X          | X                                 | X         | X         | X         |            | X          | X           | X           | X          | X          |                  |                    |  |

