## 9. STATISTICAL CONSIDERATIONS

A statistical analysis plan (SAP) will be finalized prior to database lock. Any changes from the statistical analyses described in this document will be described in the SAP, and any deviation from the final SAP will be described in the final report.

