#### 9.4.1. Efficacy Analyses

Efficacy analyses will be performed in ITT population. If the primary endpoint, (Day 14 OSI), is significant, the 4 key secondary endpoints will be sequentially tested in the order listed below. If

any null hypothesis is not rejected in this sequence of tests, formal sequential testing will be stopped and the analyses of any endpoints thereafter will be nominal only.

- Time to recovery defined as improvement from baseline score of 3 to  $\geq 4$  or from a baseline score of 4 to  $\geq 5$
- Proportion of patients with at least a 2 point improvement (increase) in the Ordinal Scale from baseline to Day 7.
- Proportion of patients with at least a 1 point improvement (increase) in the Ordinal Scale from baseline to Day 7
- Proportion of patients with at least a 1 point improvement (increase) in the Ordinal Scale from baseline to Day 14.
- Time to an improvement of 2 point using WHO Ordinal Scale Improvement (TTCI-2)
- Time to clinical improvement (TTCI-1): defined as the time from randomization to an improvement of 1 point on the Ordinal Scale
- Overall Death rate on Day 28 (DR)
- Rate of mechanical ventilation (RMV)

The difference in binary endpoints between treatment arms will be calculated with a 95% confidence interval (CI). Comparison of these endpoints between the 2 treatment arms will be performed using the Cochran-Mantel-Haenszel (CMH) test stratified by the randomization stratification factors. The CMH estimate of the odds ratio and its 95% CI and the p-value for testing the treatment difference will be reported.

The analysis of time to event endpoints will be performed by treatment arm based on a log-rank test. The median will be estimated with a 95% CI for each treatment arm using the Kaplan-Meier method. Hazard ratios with the associated 95% CI will be estimated by a stratified Cox proportional hazards model, using Efron's method of tie handling, with treatment as the factor. The strata will be the same stratification factors used for randomization.

Analyses of all other secondary endpoints will be nominal only. Details will be specified in the SAP.

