## 2. STUDY DESIGN

### 2.1 Overview of Study Design

This is a randomized phase 2 single-blinded study of low dose selinexor versus placebo to evaluate the activity and safety, as well as reduction in mortality in patients with severe COVID-19.

A dose of 20 mg selinexor or matching placebo will be administered orally on Days 1, 3, and 5 of each week for up to 2 weeks. If the patient is tolerating therapy and clinically benefitting, dosing can continue for an additional 2 weeks.

The study population will consist of hospitalized patients  $\geq 18$  years old with COVID-19.

The randomization under protocol version 6.0 or above will be stratified by:

- Use of concomitant therapies
  - Use of anti-viral (e.g. remdesivir) only
  - Use of anti-inflammatory (e.g. hydroxychloroquine, biologics targeting e.g. IL-6 or IL-1) only
  - Use of both anti-viral and anti-inflammatory therapies
  - Use of neither anti-viral nor anti-inflammatory therapy
- Number of high-risk comorbidities.
  - No high-risk comorbidity
  - One high-risk comorbidity
  - Two or above comorbidities

[figure not shown]
High risk comorbidities are defined as: BMI > 30, cancer patients on chemotherapy, patients with cardiac (CAD, AMI, CHF) or pulmonary (COPD, emphysema) disease, diabetes, hypertension.

Note: acetaminophen and nonsteroidal anti-inflammatory drugs (NSAIDs) will not constitute anti-inflammatory agents for the purposes of stratification.

The study schedules are presented in Table 1 of the protocol.

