To evaluate improvement in additional clinical measures across the 2 treatment arms	
 
• Time to recovery defined as improvement from baseline score of 3 to <math>\geq 4</math> or from a baseline score of 4 to <math>\geq 5</math>
 
• Proportion of patients with at least a 2 point improvement (increase) in the Ordinal Scale from baseline to Day 7.
 
• Proportion of patients with at least a 1 point improvement (increase) in the Ordinal Scale from baseline to Day 7
 
• Proportion of patients with at least a 1 point improvement (increase) in the Ordinal Scale from baseline to Day 14.
 
• Time to an improvement of 1 point on the Ordinal Scale (TTCI-1)
 
• Overall Survival
 
• Overall death rate on Day 14
 
• Rate of ICU admission
 
• Length of hospitalization
 
• Length of ICU stay
 
• Duration of mechanical ventilation
 
• PaO2:FiO2 and/or oxygenation index over time
 

To determine the anti-inflammatory and immune effect of selinexor	
 
• Reduction of C-reactive protein (CRP)
 
• Reduction in ferritin levels
 
• LDH
 
• Measure changes from baseline of blood plasma cytokines: IL-1<math>\beta</math>, IL-1R<math>\alpha</math>, IL-2, IL-4, IL-5, IL-6, IL-7, IL-8, IL-9, IL-10, IFN<math>\gamma</math>, IP10, TNF<math>\alpha</math>
 

To assess safety and tolerability of selinexor [time frame: up to 28 days]	
 
• Listing and documentation of frequency and severity of adverse effects
 

To characterize selinexor pharmacokinetics	

Selinexor PK parameters, maximum plasma concentration (<math>C_{max}</math>) and trough concentration (<math>C_{trough}</math>), if feasible

Exploratory Endpoints	
CCI 	

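### The primary Day 14 responder test leaves out the baseline ordinal score that sets each patient's response threshold, and that score is not among the listed baseline characteristics

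*SAP*

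**What the plan says.** The planned primary test is the same in both documents. SAP 7.1: "Comparison between 2 treatment arms will be performed using the Cochran-Mantel-Haenszel (CMH) test stratified by the randomization stratification factors". Protocol synopsis, Efficacy Analyses: "Comparison of OSI rates between the 2 treatment arms will be performed using the Cochran-Mantel-Haenszel (CMH) test stratified by the randomization stratification factors". Protocol 9.4.1 applies the same test to the binary endpoints generally.

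The strata come from SAP 2.1: "The randomization under protocol version 6.0 or above will be stratified by" concomitant therapy (four classes) and number of high-risk comorbidities (three classes), which makes 12 cells. Baseline ordinal score is not a factor there or in protocol 4.4.

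The score is available. Protocol Table 1 collects it at screening and then "Daily and the day after discharge". SAP Table 6 measures the two-point gain from it: "Baseline score is defined as the last score measured before first dosing".

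Baseline scores are expected to be mainly 3 and 4. Protocol 4.1 admits patients on supplemental or high-flow oxygen, and 4.2 excludes non-invasive positive pressure ventilation and intubation. SAP Table 1 builds a further endpoint on the same two scores: "Time to recovery defined as improvement from baseline score of 3 to" at least 4, or from 4 to at least 5.

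The score is not in the baseline characteristics of SAP 6.2, a list that is worded as non-exhaustive. It is not in the disease history (6.4) or the subgroups (7.1.2). The sensitivity analyses in 7.1.1 vary how the baseline score is defined but do not adjust for it.

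**The concern.** The baseline score decides how far each patient has to climb to count as a responder, and the comparison of arms then ignores it. If the score predicts response, the test carries outcome variation that data already collected could remove, and power is lost.

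The direction and strength of the relation cannot be read from the documents. Patients at 3 start sicker, but patients at 4 must reach a higher state.

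There is also a reporting gap that needs no assumption about prognosis. Randomization does not balance the score and no listed table shows it. The summaries of PaO2:FiO2 (SAP Table 6 and 7.2.2) and of oxygen saturation (8.3) would show a difference in starting severity only indirectly.

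**Working it through.** **1. Inputs.** From the documents: 247 planned ITT patients (protocol synopsis); about the first 50 ITT patients at 2:1 and the rest at 1:1 (SAP 7.1.1); 12 strata (SAP 2.1); 80% power as the re-estimation target (protocol 9.6). Assumed: two-sided 5% level, response rates, the share at score 3, and the odds ratio (OR) of response for score 4 against score 3.

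**2. The plan's own figure.** The basis for 247 is redacted (protocol 9.2), so it cannot be reproduced. Solving back at 1:1 with pooled variance, 40.0% against 57.7% gives n per arm = [1.96√(2×0.4885×0.5115) + 0.842√(0.400×0.600 + 0.577×0.423)]² / 0.177² ≈ 124, or about 247 in all for 80% power. The readable design numbers are consistent: 74/247 = 30%, 124/247 = 50%, 371/247 = 1.5.

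**3. Analytic gain.** Adjusting for a binary score divides the noncentrality by √(1−R²), with R² = s(1−s)d²/[p(1−p)]. Here s is the share at score 3, d the response gap between scores, and p the overall rate. Take s = 0.30, p = 0.50 and base power 80% (noncentrality 1.96 + 0.842 = 2.80).
- d = 0.20 (OR about 2.3): R² = 0.21×0.04/0.25 = 0.034; 2.80/0.983 = 2.85; power 81.3%, gain 1.3 points.
- d = 0.30 (OR about 3.5): R² = 0.076; 2.80/0.961 = 2.91; power 83.0%, gain 3.0 points.
- d = 0.40 (OR about 5.8): R² = 0.134; 2.80/0.930 = 3.01; power 85.3%, gain 5.3 points.

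Over s from 0.2 to 0.5, a 3-point gain needs a gap of about 27 to 34 percentage points, an OR of about 3.1 to 4.6.

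**4. Simulated gain.** Simulation A: 50 patients at 2:1 then 1:1, 12 blocked strata, 35% at score 3, placebo response 55%, treatment OR 2.1, strata not prognostic, logistic score test; each test uses the critical value that gives it a true 5% level. Simulation B: 1:1, marginal rates fixed at about 80% power with control rate 40%, and score added to the 12 strata in a linear model.

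| Score OR | CMH power, A (nominal level) | Gain, A | Gain, B (30% / 50% at score 3) |
|---|---|---|---|
| 1 | 79.0% | +0.1 | +0.3 / +0.1 |
| 2 | 77.1% | +1.0 | +0.9 / +1.3 |
| 3 | 74.0% | +2.5 | +3.0 / +2.6 |
| 4 | 70.8% | +4.4 | +3.9 / +4.5 |
| 5 (A), 6 (B) | 67.6% | +6.0 | +5.2 / +6.8 |

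Variations on A: with 15% or 50% at score 3 and OR 3, the gain is +1.6 or +2.7. If score 4 is the less likely to respond (OR 1/2, 1/3), it is +0.8 and +1.7. If the share at score 3 varies from 5% to 67.5% across therapy classes, it is +0.9 at OR 2 and +2.0 at OR 3.

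**5. Level when the score is omitted.** Null rejection of the planned CMH is 4.9 to 5.1% in A and 4.6 to 5.3% in B, including strongly prognostic scores. The adjusted test gives 5.2 to 5.5% in A and 4.7 to 5.1% in B.

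**6. Imbalance.** The 2:1 then 1:1 scheme gives arms of 33.3 + 98.5 = 131.8 and 16.7 + 98.5 = 115.2. With 35% at score 3, the SD of the arm difference in that share is √[0.35×0.65×(1/131.8 + 1/115.2)] = 6.1 points, so a difference above 10 points occurs in about 10% of trials (3% at a 15% share, 12% at 50%). With 30% at score 3 and equal arms the SD is 5.8 points. A 1.96-SD imbalance with a 30-point response gap then shifts the observed rate difference by 1.96×5.8×0.30 = 3.4 points.

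**7. Crossing the score into the CMH.** This makes 24 strata of 247/24 = 10 patients on average. Power changes by −2.0 points at OR 1, −1.3 at OR 2 and +0.5 at OR 3 (A, nominal level).

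**8. Allocation switch.** Early patients are 33.3/131.8 = 25.3% of one arm and 16.7/115.2 = 14.5% of the other. If response drifted from 40% to 60% (assumed), the rate difference shifts by 0.108×20 = 2.2 points. Simulated null rejection is then 5.5 to 5.6% for the CMH, 5.8 to 6.2% for the score-adjusted model and 4.7 to 5.2% with a period term added. In A the period term costs 0.5 to 0.8 power points.

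**The case against.** A stratified CMH on the randomization factors is a standard, prespecified choice for a binary phase 2 endpoint, and the protocol names it. The gain is unknown because the inputs are not given. Lower baseline severity and a higher target may offset each other and put the score OR near 1 to 2, where the gain is at most about 1 point. The proposed change also makes the odds ratio conditional beside a marginal rate difference, alters the interim programming, and may be slightly liberal. All of this stands, and it is why the point concerns efficiency and reporting. It does not argue against tabulating the score or against a prespecified adjusted sensitivity analysis.

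Three stronger readings are tempting, and none is supported.

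- A reader might infer that omitting the score biases the test or inflates its error rate. Step 5 shows that it does not.
- A reader might infer that the plan refuses to report the score. The list in SAP 6.2 is not exhaustive and the exploratory sections are redacted, so the score is unlisted, not excluded.
- In the other direction, a reader might take the planned CMH as valid without limit. Step 5 covers only omission of the score. Neither the CMH nor the adjusted model without a period term accounts for the change from 2:1 to 1:1. SAP 7.1.1 treats that change as non-confounding and covers it by a sensitivity analysis. Protocol 4.4 still states 2:1 while the synopsis states 1:1, and these passages must be reconciled.

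**Conclusion.** The point holds as one to consider. The primary test ignores a baseline value that is already collected and that defines each patient's target. Type I error is not harmed by this.

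The power given up is about 0 to 1 point if the score OR is 1 to 2, about 2.5 to 3 points at 3, and 4 to 6 or more at 4 and above. These figures rest on assumed response rates, baseline split and prognostic strength. The analytic approximation and both simulations agree closely, but the documents cannot say which row applies. A meaningful arm imbalance in the score is plausible and could go unseen.

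**What to change.** Before any unblinded data are seen:

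- Prespecify for OSI2-14 a main-effects logistic regression with treatment, the two randomization factors and baseline ordinal score (3 or 4, with a stated rule for any other score). Preferably make it the primary test, keep the planned CMH as a sensitivity analysis, and use the same statistic for conditional power and the CHW test. At minimum, add the model as a prespecified sensitivity analysis.
- Fit the same model with an allocation-period term, and describe neither test as valid with respect to the ratio change unless period is accounted for.
- Keep the planned rate difference with its 95% CI, and label the model's odds ratio as conditional.
- List baseline ordinal score by arm in SAP 6.2, and state which score is baseline for ITT patients who are never dosed.
- Do not cross the score into 24 CMH strata: about 2 points are lost if it is not prognostic.

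**Cost.** No new data. Because the protocol names the CMH, protocol section 9 governs the change: "Any changes from the statistical analyses described in this document will be described in the SAP". SAP 7.1, SAP 6.2 and the interim programming change. The conditional odds ratio sits further from 1 (simulated median 2.15 with the score against 2.04 without it at score OR 3). The level may reach about 5.5%, the period term costs under 1 power point, and there is no gain if the score is not prognostic.
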